Study Protocol

Official Title of the Study:

Forgetting Alcohol: A Double-blind, Randomized Controlled Trial Investigating Memory Inhibition Training in Young Binge Drinkers

NCT ID: not yet assigned

Date: February 5, 2019

Study Design and Setting

The present study will be composed of three different phases: 1) behavioral and electrophysiological analyses of MI abilities in young BDs as compared to age-matched non/low-drinkers; 2) a double-blind, randomized controlled trial (RCT) aiming at assessing the effects of a MI training protocol at the behavioral and electrophysiological level; and 3) monitoring of self-reported alcohol consumption and alcohol craving 10 days and 3 months after the MI training.

Target population

The volunteers will be ninety college students (~50% female), aged between 18 and 23 years: 45 non/low-drinkers and 45 BDs matched for age and gender. All participants will be recruited through a screening questionnaire administered in the classroom of several courses taught at the University of Minho (UM). The screening will include the Alcohol Use Disorder Identification Test (AUDIT) [1] along with other questions concerning alcohol and drugs use.

Inclusion and exclusion criteria

To participate in the study, college students must meet the following eligibility criteria: report (i) drinking 5 or more drinks on one occasion at least once a month, and (ii) drinking at a speed of at least two drinks per hour during these episodes (which brings blood alcohol concentration to 0.08 gram percent or above [2], in order to be classified as BDs; or report (i) never drinking 5 or more drinks on each occasion and (ii) having an AUDIT score ≤ 4 , to be considered as non/low-drinkers. The students who fulfilled the inclusion criteria will perform a clinical interview that will assess the following exclusion

criteria: a) use of illegal drugs except cannabis (as determined by the Drug Use Disorders Identification Test-Extended [DUDIT-E], [3]); b) alcohol abuse (i.e., AUDIT \geq 20); consumption of medical drugs with psychoactive effects (e.g., sedatives or anxiolytics) during the two weeks before the experiment; c) personal history of psychopathological disorders (according to DSM-V criteria); d) history of traumatic brain injury or neurological disorder; e) family history of alcoholism or diagnosis of other substance abuse; f) occurrence of one or more episodes of loss of consciousness for more than 20 minutes; g) non-corrected sensory deficits; h) Global Severity Index (GSI) $>$ 90 (Symptom Checklist-90-Revised questionnaire [SCL-90-R], [4]) or a score above 90 in at least two of the symptomatic dimensions.

Quality assurance and randomization

The protocol will be implemented by three skilled researchers with expertise in behavioral and EEG assessments and tDCS interventions. Researchers will not be aware of the results of the pre-training EEG assessment and will be blind to the randomization procedure that will follow. The randomization of the BD groups will be performed by an independent researcher using Microsoft Excel. BDs will receive one of the following interventions: 1) Combined training (verum CT and tDCS applied over the right dorsolateral prefrontal cortex); 2) Cognitive training (active CT and sham tDCS); or 3) Control (sham CT and sham tDCS). Based on this experimental procedure, it is expected that researchers will be able to answer the following research questions:

1. How does BD affect alcohol-related MI in young adults? Namely, are the behavioral and electrophysiological MI mechanisms - specifically those related to the suppression of alcohol-related memories - altered in BDs when compared to non/low-drinkers?

2. What is the effect of a MI training on behavioral TNTA task performance?

Specifically, will the BDs show a reduced recollection of no-think images - mainly for alcoholic no-think images – after training?

3. Are the electrophysiological correlates underlying MI mechanisms and alcohol cue reactivity changed by MI training?

4. Will the MI training reduce alcohol consumption and craving levels at 10-day and 3-month follow-ups?

Experimental tasks

Alcohol Cue Reactivity (ACR) task

Firstly, the participants will perform the ACR task. In this task, each trial starts with a white fixation cross in a grey background for a variable duration ranging from 1000 to 1500 ms. Subsequently, an alcoholic or non-alcoholic image is randomly presented at the center of the screen for 3000 ms. Participants are asked to be focused on the fixation cross and then to look at the image whenever it appears. After the visualization of each image, participants have to register their emotional responses in terms of valence and arousal using the Self-Assessment Manikin [5]. The full task includes a total of 80 trials with 40 alcoholic and 40 non-alcoholic images obtained from the Amsterdam Beverage Picture Set [6]. This task has the purpose of assessing the emotional response and electrophysiological reactivity of participants to alcohol cues.

TNTA task

The TNTA task is a version of the classical Think/No-Think paradigm [7], which was specially developed to examine MI mechanisms in alcohol-related contexts [8]. This task includes thirty-six pictures (18 related to alcohol and 18 non-related to alcohol) from

the Galician Beverage Picture Set (GBPS) [9] and 36 images of neutral objects obtained from the POPORO database [10]. The GBPS is a database of alcohol and non-alcohol pictures embedded in real-life scenarios which comprises 6 types of beverages: beer, wine, and liquor (alcoholic drinks), and water, juice, and milk (non-alcoholic drinks). The TNTA task includes 6 images from each of the 6 beverages. The pictures also differ in terms of orientation (vertical or horizontal) and number of people (no people, 1 person, 2 or more people). As such, within each type of beverage, 3 are vertical (each one with a different number of people: 0 people, 1 person, 2 or more people) and the other 3 are horizontal (also with 0 people, 1 person, 2 or more people). The task is divided into three phases, i.e., 1) the Learning phase, 2) the Think/No-Think (TNT) phase and 3) the Memory-Test phase, which are carefully described below.

Learning Phase

During the Learning phase, participants are asked to memorize 36 image-pairs (i.e., a neutral image paired with an image including alcoholic or non-alcoholic drinks) divided into three blocks of 12 pairs. Each block starts with the presentation of the 12 image-pairs at the center of the screen, each for 4000 ms, in a randomized order, and with an inter-stimuli interval (ISI) ranging from 1000 to 2000 ms. When the presentation of the 12 pairs finished, each of the neutral images are presented for 2000 ms, and the participants must try to remember the image that was associated with the neutral object through three questions: Q1. “Which beverage was associated with this picture?”; Q2. “How was the picture oriented?”; Q3. “How many people were there in the picture?”. In each block, the 12 pairs and the questions are repeated three times. At the end of each block, feedback with the total number of correct responses will be provided. Correct recall will only be considered when participants provide the right answer to the 3 questions.

Thus, the combination of the potential answers to the 3 questions ($6 \times 2 \times 3 = 36$) ensured that each target image displayed a unique combination.

TNT Phase

In this phase, there are two possible actions: to Think or to No-Think on the alcoholic/non-alcoholic image paired with the neutral object previously. Specifically, in the Think condition – determined by a green frame that circumvents the neutral image -, participants will be asked to focus on the neutral image and think in the alcoholic/non-alcoholic image that was associated with it (i.e., the one that was paired with this specific neutral image). In the No-Think condition - determined by a red frame that circumvents the neutral image -, participants are instructed to focus on the image and to not let the previously associated alcoholic/non-alcoholic picture enter their consciousness. All the images will be presented for 3000 ms and randomly repeated 10 times and presented for four seconds at the center of the screen with an offset-onset ISI ranging from 1100-1300 ms. From the initial set of 36 neutral images shown in the learning phase only 24 will be depicted during the TNT phase, 12 in each condition (i.e., Think vs No Think). The remaining 12 neutral images not depicted in this phase will serve as a baseline condition for the following Memory-Test phase of the task.

Memory -Test Phase

During this phase, the 36 neutral images from each pair are again presented, including the 12 images of the baseline condition which are not presented during the TNT phase. Participants are asked to remember the image (alcoholic or non-alcoholic) that was initially associated with the neutral object through the same three questions of the Learning phase. Three different versions of the task (where all the pictures were part of

the three conditions: Think, No-Think and baseline) will be created and counterbalanced across participants.

TNTA task variations for active and false cognitive training

Two variations of the TNTA task were developed for the active cognitive training and for the false cognitive training. The stimuli employed in these variations of the TNTA task were also obtained from the GBPS and POPORO databases; however, these stimuli differ from those used in the original TNTA task. The structure of the task for the MI active cognitive training is the same as the original TNTA task. However, in this variation, the Learning phase is only composed of two blocks of 12-image pairs, and in the TNT phase, all the stimuli to be inhibited are alcohol-related images.

In the false cognitive training version, the Learning phase also have only two blocks of 12-image pairs. However, the TNT phase is replaced by a Forced-Choice Reaction Time (FCRT) task, during which the participants only must categorize alcoholic and non-alcoholic images answering to the question “What type of beverage was there in the image?” (answer: “Alcoholic drink” or “Non-alcoholic drink”).

All the computerized tasks will be programmed in open-source software Psychopy [11].

Procedure

T1: Clinical Interview

During this interview, we will verify the fulfillment of the exclusion/inclusion criteria and assess the baseline levels of some constructs (e.g., craving levels, impulsivity). Consequently, we will use the following instruments: *1)* the AUDIT along with five additional alcohol use questions (i.e., speed of drinking [number of drinks

consumed per hour], number and type of drinks consumed in a standard week, percentage of times getting drunk when going out, age of onset of regular and BD) to assess participants' drinking patterns; 2) the DUDIT-E to examine the consumption of other drugs; 3) the Penn Alcohol Craving Scale (PACS) and the Alcohol Craving Questionnaire-Short Form Revised (ACQ-SF-R) to assess the alcohol craving; 4) the Barratt Impulsivity Scale-11 (BIS-11) and the short form of the Urgency-Premeditation-Perseverance-Sensation Seeking-Positive Urgency (UPPS-P) impulsive behavior scale to assess participants' impulsiveness; 5) the Symptom Checklist-90-Revised questionnaire (SCL-90-R) to evaluate the presence of psychopathological traits; 6) a clinical history interview to explore the personal/family history of psychopathological and neurological disorders as well as the overall medical history of the participants; and 7) the Edinburgh Handedness Inventory (EHI) to evaluate the participants' handedness.

T2: Pre-training EEG Assessment

During the pre-training EEG assessment, psychological (i.e., craving levels), behavioral (i.e., alcohol consumption levels and task performance) and neurofunctional (e.g., ERPs, brain FC) outcomes will be assessed. EEG data will be collected while participants perform the ACR and the TNTA task. Before the EEG recording, participants will be asked to perform a breathalyzer test to ensure that blood alcohol concentration value is 0.0% (Alcoscan ALC-1). Along with the AUDIT, and in order to determine alcohol consumption levels during the previous week and the previous three months, we will administer the Alcohol Timeline Followback (TLFB) and the Typical and Atypical Drinking Diary (TADD), respectively. After filling in the questionnaires, participants will perform the ACR task. Participants' resting brain activity will be recorded for three minutes during eyes-closed prior to the TNTA task. Finally, they will perform the TNTA

task. The total duration of the pre-training EEG assessment will be approximately two and a half hours.

EEG data will be recorded using the ActiveTwo Biosemi System (Biosemi, Inc.) from 64 electrodes placed according the 10-10 system [12] and digitized at a 512 Hz rate. Vertical and horizontal electrooculogram activity will be recorded to control for eye movements and blinks. Two additional electrodes will be placed on the mastoids, bilaterally, to provide the signal offline reference. Electrode impedances will be kept below 20 kΩ and the EEG signal will be filtered on-line with a 0.01–100 Hz band pass filter.

T3: MI Training Sessions

After the pre-training EEG assessment (T2), BDs will be randomly assigned to one of the three training subgroups: *a) Combined training; b) Cognitive training; or c) Control*. The participants' allocation to the training group will be done by an independent researcher who will be responsible to program the tDCS parameters. Thus, both participants and research team will be blind to the randomization procedure.

During T3, subjects will perform the variation of the TNTA task corresponding to the group to which they will be assigned. After the first phase of the task (i.e., Learning Phase), neuromodulation (sham or active) will be performed using tDCS - a non-invasive, painless and safe brain stimulation method capable of modulating cortical excitability through a weak constant electric current induced from two surface electrodes placed on the scalp [13]. Twenty minutes of 2 mA direct current will be applied to the scalp using a saline-soaked pair of 35 cm² surface sponge electrodes, through an Eldith DC Stimulator Plus (Neuroconn, Germany). To stimulate the right DLPFC, the anodal electrode will be placed over F4 according to the 10-20 international system for EEG electrode placement.

The cathode electrode will be placed over the contralateral supraorbital area. During the active simulation, the current will fade in for 15 seconds, will be constant at 2 mA for 20 minutes, and then will fade out for 15 seconds. During the sham stimulation, the electric current will fade in during 15 seconds until reaching 2 mA, then will be constant at 2 mA for 15 seconds and will fade out for 15 seconds. This procedure makes both active and sham stimulation indistinguishable for the participants. Before and after the training sessions, participants will answer to a continuous Visual Analog Scale that allows checking for possible secondary effects of the electrical stimulation.

T4: Post-training EEG Assessment

At T4, participants will perform the ACR and TNTA tasks under the same procedure to the one undertaken during the T2.

T5: Monitoring of alcohol consumption and alcohol craving.

Ten days after the post-training EEG assessment, the primary craving and alcohol consumption outcomes will be assessed. For this purpose, we will administer the PACS, the ACQ-SF-R and the AUDIT. Additionally, three months post-intervention, BDs will answer the same questionnaires and also the TADD aiming at assessing medium-term effects of the MI training in the alcohol craving and consumption levels.

Management and Ethics

Ethical requirements for human research will be followed in full accordance with the Code of Ethical Principles for Medical Research Involving Humans Subjects outlined in the Declaration of Helsinki (64th World Medical Association General Assembly, Brazil, 2013). The Ethics Committee for Social and Human Sciences of University of

Minho approved the present protocol in December 12, 2018 (approval reference: CE.CSH 078/2018). Prior to enrolling in the study, subjects will be informed about the aims, conditions and procedure of the study. Two copies of the informed consent forms will be provided, both of which will be signed by the researchers and participants. It is researchers' responsibility to guarantee the anonymity of the participants and the confidentiality of the data. The files containing data from the participants will be identified by the participant's code, not the name. The document containing the records of participants' personal information (e.g., names, contacts, code) will be stored in a different location from the data files and will only be accessible to authorized researchers. All files will be password protected and stored by the researchers in secure locations. Participants will be able to cease their participation in the study at any time without any consequences related to the relationship between the research team, the participant and the university. If participants want to terminate their enrollment in the study or ask for their data to be deleted later, researchers will promptly erase all data from files and eliminate documents using a paper shredder. There are no risks associated to the research protocol. College students will receive gift vouchers in order to compensate for their participation.

References

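### The described masking supports a double-blind claim for Combined versus Cognitive only: Control receives a visibly different training task that nothing hides from T3 staff

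*Protocol*

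**What the plan says.** The Protocol's title describes the trial as "A Double-blind, Randomized Controlled Trial Investigating Memory Inhibition Training in Young Binge Drinkers". Three parts of the Protocol support that label.

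- **Quality assurance and randomization.** "The randomization of the BD groups will be performed by an independent researcher using Microsoft Excel". The three researchers who implement the protocol "will be blind to the randomization procedure that will follow".
- **T3: MI Training Sessions, allocation.** "The participants' allocation to the training group will be done by an independent researcher who will be responsible to program the tDCS parameters". The next sentence draws the conclusion: "Thus, both participants and research team will be blind to the randomization procedure".
- **T3, sham current.** After describing the sham waveform, the Protocol states: "This procedure makes both active and sham stimulation indistinguishable for the participants".

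The arms differ in task as well as current. Combined has active training with active tDCS, Cognitive has active training with sham tDCS, and Control has sham training with sham tDCS. The section on TNTA task variations says the active version keeps the structure of the original task, whereas in the false version "the TNT phase is replaced by a Forced-Choice Reaction Time (FCRT) task", and participants only classify drinks as alcoholic or not. Under Management and Ethics, "subjects will be informed about the aims, conditions and procedure of the study".

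**The concern.** The conclusion in T3 covers everyone and the whole intervention, but the reason given for it concerns allocation and the electrical stimulation. A sham waveform cannot conceal which task is on the screen. Anyone who instructs or watches a Control session sees no Think/No-Think phase.

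The comparison affected carries the main efficacy claim. The SAP Abstract expects benefit after both Combined and Cognitive training, so the evidence that training works comes from comparison with Control. Section T5 calls craving and alcohol consumption primary and measures them at 10 days with the PACS, ACQ-SF-R and AUDIT, adding the TADD at 3 months. All are self-reports and open to expectation. If these contrasts are published as double-blind, readers will discount expectation effects more than the design allows.

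**Working it through.** The documents state no figure to reproduce here. The main check sets each masking measure against what it can hide.

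**Step 1: what each measure covers**

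| Measure (Protocol section) | Hides | Does not hide |
|---|---|---|
| Independent randomisation in Excel (Quality assurance and randomization) | The upcoming assignment | The task delivered |
| Independent researcher allocates and programs tDCS (T3) | Active or sham current, from the team | The task delivered |
| Sham ramp-up and ramp-down (T3) | Active or sham current, from participants | The task delivered |
| Sham training with two learning blocks of 12 pairs and the same image databases (TNTA task variations) | Differences in the Learning phase and source of images | Replacement of the Think/No-Think phase |

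**Step 2: apply this to each comparison**

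| Comparison | Task | Current | Covered by the described masking? |
|---|---|---|---|
| Combined vs Cognitive | Same | Differs | Yes |
| Cognitive vs Control | Differs | Same (sham) | No measure hides the task from T3 staff |
| Combined vs Control | Differs | Differs | Current yes, task no |

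**Step 3: staff.** Three researchers implement the protocol. Nothing says that the independent researcher launches the task, that the screen is hidden, or that T4 and T5 staff differ from T3 staff. The SAP Abstract gives three sessions on three consecutive days, so the task is visible to staff repeatedly.

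**Step 4: participants.** Each sees one training version. All binge drinkers did the full Think/No-Think task at T2, before randomisation, and all are given information on the study. A Control participant could notice that the suppression phase has gone. The only check described is a visual analogue scale for side effects of stimulation; no allocation-guess or expectancy question appears.

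**Step 5: illustrative size.** Assumptions, none of them in the documents: equal arms (45/3 = 15), a two-sided two-sample t-test at 0.05, no true effect, and an expectation bias of d standard deviations favouring the trained arm.

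- Noncentrality = d × √(15 × 15 / 30) = d × 2.739, with 28 degrees of freedom and critical value 2.048.
- d = 0.2: noncentrality 0.548, rejection probability 8.3%.
- d = 0.3: noncentrality 0.822, rejection probability 12.5%.
- d = 0.5: noncentrality 1.369, rejection probability 26.2%.

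A three-group F test (2 and 42 degrees of freedom) with both trained arms shifted by d has noncentrality 15 × d² × 2/3, that is 0.40, 0.90 and 2.50. The rejection probabilities are 7.9%, 11.8% and 25.7%, so the choice of test changes little.

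**The case against.** **The sham training is a real masking device.** It shares the two-block Learning phase and the image sources with the active version, and randomisation is independent. A reader might infer that the blinding rests on tDCS programming alone; the documents do not support that. What stands is that none of these features hides the replaced phase from the person running T3.

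**Participants may not know their arm.** A reader might infer that Control participants are unblinded. The documents do not establish this. Seeing a task is different from knowing that it is the inactive one. The ethics wording is general, its reference to conditions may mean conditions of participation, and the consent pages are not available. Participant blinding is therefore unverified, which is weaker than shown to fail.

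**Some outcomes are less exposed.** Recall in the TNTA task is collected by computer and scored by a fixed three-question rule, leaving little room for assessor influence, although effort could still differ. This limits the concern mainly to self-reported outcomes.

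**The size is hypothetical.** The bias values have no source in the documents. Pooling both trained arms (30 versus 15) gives 9.5%, 15.3% and 34.0%, but the plan contains no pooled contrast: the SAP compares the three training groups. The larger figures should not be used.

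**Conclusion.** The point holds in limited form. The double-blind label and the blanket statement in T3 are supported for Combined versus Cognitive. For Combined versus Control and Cognitive versus Control, no described measure blinds the staff who deliver T3, and blinding of participants is not assured. It would go too far to call the trial unblinded or to say that participants know their arm.

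The finding about staff follows from the task descriptions and needs no numerical assumption, though it would change if an undescribed arrangement keeps staff from seeing the task. The effect on error rates cannot be derived from the documents. The range of about 8% to 26% depends entirely on the assumed bias of 0.2 to 0.5 SD and equal arms of 15, and only shows that a moderate expectation effect could matter at this sample size.

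**What to change.** 1. **Wording.** Limit the double-blind claim to Combined versus Cognitive. State that, for comparisons with Control, T3 staff are not blinded to the task and participant blinding is not assured. If an arrangement exists that hides the task from staff, describe it, and say what participants are told about the training versions.
2. **Rota.** Have T4 and T5 for each participant run by one of the three existing researchers who did not run that participant's T3 sessions. This must be set before T3, since the separation cannot be recovered afterwards.
3. **Check.** Add a one-item allocation-guess or expectancy rating after the last T3 session and report it by arm. The existing side-effect scale cannot serve here, because it concerns the current and not the task.
4. **Interpretation.** The rota limits staff influence but leaves participant expectation untouched, so Control contrasts on self-reported craving and drinking should be reported with that limitation.

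The cost is a weaker blinding claim, a scheduling constraint within the present team and one extra question. No arm, outcome or sample-size change is needed.

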## Statistical Analysis

The first step of the statistical analyses will be to examine the behavioral and EEG correlates of MI among college BDs and non/low-drinkers. For that purpose, the outcomes of the TNTA task collected during the pre-training assessment (T2) in BDs and non/low-drinkers will be compared and correlated with alcohol consumption (AUDIT) and alcohol craving measures (i.e., the PACS' and ACQ-SF-R's scores, and the ERPs and valence/arousal ratings recorded during the ACR task). Secondly, with the purpose of verifying the impact of the *combined, cognitive* and *control* training procedures applied to BDs on psychological, behavioral and neurofunctional measures, the pre-training data (T2) from the 45 BDs will be compared with the post-training data (T4) from the same subjects. Thirdly, to examine potential differences in the psychological, behavioral and neurofunctional effects of the training sessions both in terms of MI abilities and alcohol craving/consumption, the results of the post-training assessment (T4) of the three training groups will be compared.

With regard to the behavioral data, items learned during the learning phase and correctly recalled during the memory test phase will be considered correct responses. Accordingly, the percentage of correct responses (for Think, No-Think and Baseline items) will be computed according to the following formula:

$$\left( \frac{\text{number of correctly recalled items}}{\text{number of previously learned items}} \right) \times 100$$

A mixed-model analysis of variance (ANOVA) with one between-subject factor, Group (non/low-drinkers, BDs), and two within-subject factors, Condition (Think, NoThink, Baseline) and Content (Alcohol, Non-Alcohol) will be conducted on the recall accuracy rate to examine the participants' MI ability at T2. Afterwards, a repeated-measures ANOVA with three within-factors: Moment (T2 and T4), Condition (Think, NoThink, Baseline) and Content (Alcohol, Non-Alcohol) will be performed to explore the training effects on the MI ability of BDs only.

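### The T4 memory task appears to reuse the T2 item set, so carry-over is confounded with training in the T2-T4 analyses that have no training-group factor

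*Protocol*

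**What the plan says.** Under T4: Post-training EEG Assessment, the protocol says: "At T4, participants will perform the ACR and TNTA tasks under the same procedure to the one undertaken during the T2".

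The TNTA task section describes a single assessment set: "This task includes thirty-six pictures (18 related to alcohol and 18 non-related to alcohol) from" the GBPS, each paired with one of 36 neutral objects. On versions, the Memory-Test Phase section says that three forms of the task, in which every picture serves in each condition, "will be created and counterbalanced across participants". The rotation is over conditions and the balance is over people. Nothing is said about T2 versus T4.

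Fresh stimuli are promised in one place only, for the T3 training variations: "these stimuli differ from those used in the original TNTA task".

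In the SAP (Statistical Analysis), the behavioural training model is a repeated-measures ANOVA with Moment (T2, T4), Condition and Content as within-subject factors. It "will be performed to explore the training effects on the MI ability of BDs only". Training group is not a factor. The same is true of the T2-T4 ERP models for the TNTA and ACR tasks. The SAP also announces a comparison of the three arms at T4, but gives no model for it.

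**The concern.** Research question 2 asks whether binge drinkers recall fewer No-Think images after training. The measure is recall of items that each participant first learns and then retrieves, suppresses or leaves alone. If the same items return at T4, their history at T2 is part of what T4 measures. Relearning may be faster, earlier suppression may persist, and Baseline items may no longer be untouched.

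A T2-T4 change in No-Think recall, or in the gap between No-Think and Baseline, can then come from having done the task before. The specified ANOVA would report that change as a training effect. No later analysis can restore an untouched Baseline, so the matter has to be settled before enrolment.

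**Working it through.** **1. The plan's own count.** Learning Phase section: 6 beverages x 2 orientations x 3 people levels = 36 unique answers. TNTA task section: 6 beverages x 6 images = 36 pictures. The two agree, so one set uses each answer combination exactly once.

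**2. Exposure by the end of T2.** Inputs from the Learning, TNT and Memory-Test Phase sections: 3 study presentations and 3 learning tests per pair (reading the stated repetition as three rounds in total), 10 TNT trials for 24 of the 36 items, and 1 final test of all 36.

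- Baseline cue: 3 + 3 + 1 = 7 encounters.
- Think or No-Think cue: 3 + 3 + 10 + 1 = 17 encounters.

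**3. What the version at T4 changes.** Across three versions every picture takes all three conditions, so a picture has a different condition in each version.

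- Same version at T4: all 12 No-Think items were suppressed 10 times at T2, and all 12 Think items were retrieved 10 times.
- Different version at T4: none of the 12 Baseline items was Baseline at T2. Each had 10 Think or No-Think trials. None of the 12 No-Think items was No-Think at T2.

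Under both readings all 36 pairs have been studied and tested before. The documents do not say which reading applies.

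**4. What carry-over does to the tests.** The documents give no effect size, alpha or power calculation for this outcome, so this step is an illustration. Assumptions: no training effect, two-sided alpha 0.05, 15 people per arm (45/3), and carry-over equal in all arms at c SD of a single T2-T4 change score, with c from 0 to 0.5.

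- T2-T4 test in the 45 binge drinkers: noncentral t with 44 df and noncentrality c x sqrt(45). For example, 0.2 x 6.708 = 1.342 and 0.5 x 6.708 = 3.354.
- T2-T4 test within one arm: n = 15, 20,000 simulated trials.
- Arm by Moment: one-way ANOVA of change scores in 3 x 15, 20,000 simulated trials.

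| c (SD) | T2-T4, n = 45 | T2-T4 within one arm, n = 15 | Arm by Moment |
|---|---|---|---|
| 0 | 5.0% | 4.8% | 5.0% |
| 0.2 | 25.9% | 11.2% | 5.3% |
| 0.3 | 50.3% | 19.4% | 4.8% |
| 0.4 | 74.7% | 30.5% | 4.9% |
| 0.5 | 90.7% | 43.7% | 4.8% |

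Simulation of the first test agreed with the formula to within half a percentage point. The test is two-sided, so the sign of c does not matter.

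**The case against.** The strongest reply is that the trial has a randomised sham/sham control that takes the same tasks at T2 and T4. Carry-over common to the arms cancels on average when arms are compared, and the last column of the table bears this out. On this view the false-positive risk comes mainly from the missing training-group factor, which new pictures alone would not cure. This stands. It limits the problem to the T2-T4 analyses, and it means the fix must cover the model as well as the stimuli. It does not dispose of the point. The SAP gives no model for the arm comparison, and cancellation neither restores an untouched Baseline nor protects against carry-over that differs with training.

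A second reply is that the T4 section speaks of the same procedure, not the same pictures. That is fair: reuse is an inference. It is the natural one, because a single assessment set is described and different stimuli are specified only for training. If it is wrong, the T4 set, version and pairings are unspecified and still need to be stated.

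Third, a reader might infer that T2 suppression must lower No-Think recall at T4. The documents do not support a direction. T4 re-teaches every pair before the TNT phase, which could push recall the other way.

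Fourth, a reader might infer that over-learned pairs leave recall near its ceiling. The SAP scores recall as a percentage of the items learned beforehand. Faster learning raises that denominator and does not by itself show that the scored percentage is close to 100. Reduced sensitivity is possible but not demonstrated.

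**Conclusion.** The point holds in a limited form. On the natural reading of the protocol, T4 re-tests pairs already used at T2, and the specified T2-T4 ANOVAs in binge drinkers cannot tell carry-over from training. Its size and sign are unknown. If it is zero, the T2-T4 test keeps its 5% error rate; under the assumed 0.2 to 0.5 SD, that test rejects in 25.9% to 90.7% of trials with no training effect. These rates rest entirely on the assumptions stated with them.

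A reader might conclude that the trial cannot attribute any change in memory inhibition to training. The documents do not support that. A properly modelled comparison with the control arm remains valid for carry-over that is equal across arms. What remains there is a Baseline that is no longer untouched and a possible loss of sensitivity. The change is worth making before enrolment because it is cheap then and cannot be made afterwards.

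**What to change.** State in the protocol which pictures, version and pairings each participant receives at T4. Preferably:

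- Prepare a parallel assessment set B: 36 new neutral objects paired with 36 GBPS pictures used in neither set A nor training, in the same 6 x 2 x 3 structure, with its own three versions.
- Assign set order (A then B, or B then A) before T2. Arms are allocated only after T2 (T3: MI Training Sessions), so order cannot be assigned within arm; stratify the later randomisation by set order instead.
- Split the non/low-drinkers between A and B at T2.
- Include set order in the model.
- If too few unused GBPS pictures remain (the documents do not give the size of the database), use new neutral objects and new pairings at T4. This reduces carry-over but leaves the pictures familiar.

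In either case, base the training conclusion on the training group by Moment interaction (with Condition and Content), not on the pooled T2-T4 change, and write that model into the SAP.

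Cost: stimulus preparation, three more task files and one extra model term, with no added visits or participants. Some between-set difficulty variance enters. Balancing order protects the mean difference, while the variance is removed only so far as set order is modelled. With an assumed 15 per arm, the orders split 7 and 8, and two orders by three versions give 15/6 = 2.5 people per cell, so balance within an arm will be approximate.
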